Outpatient cardiology and internal medicine providers in the Yale health system will be selected for potential participation in the study based on the frequency with which they see patients who meet the inclusion criteria (must see at least 10 potentially eligible patients per week). They will be identified based on a retrospective review of clinical encounters that include patients at very high risk for ASCVD events based on clinical guidelines within Epic and approached for consent to participate in the study. Once consented, we will determine baseline prescribing patterns for lipid lowering therapy (over 3months) specifically looking at the proportion of very high risk ASCVD patients on high-intensity statin therapy, ezetimibe, or PCSK9 inhibitor as well as distribution of LDL-C. All physicians will then be randomized within Epic to either the intervention group or the control (usual care) group via a permutated block randomization scheme to ensure an equal number of providers in each study arm. Logic checks within the alerts ensure that once a provider is assigned to an arm, they remain in that arm for the remainder of the study. This will create 100 clusters (providers) to which eligible patient participants will be assigned upon their outpatient visit. In other words, any patient seen by a provider randomized to the intervention (alert) group will have an informational alert generated when their provider opens the order entry screen in the patient's medical record. On the contrary, any patient seen by a provider randomized to the control arm will not generate an alert and will receive usual care. Instead, a "silent alert" that simply registers the patient into the trial by the study team is generated. Because it is likely that providers may internalize the best practice metrics once repeatedly exposed to the alert, cluster randomization of patients at the level of the provider will ensure that providers consistently receive an alert or not, which will reduce contamination between study arms. It will also minimize the chance that providers get so accustomed to seeing an alert for hyperlipidemia that they will become less attentive to the condition in patients not generating an alert. Additional pre- and postintervention analyses in the control group, leveraging the three-month baseline period, can assess the level of contamination and the effect of secular trends towards better care over time.

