Our primary outcome will be proportion of patients with intensification of lipid lowering therapy, defined by an increase in statin dose, addition of ezetimibe, or addition of PCSK9 at 90-days. The key secondary endpoint will be the achieved LDL-C (fasting or non-fasting¹¹) at 6-months. Other outcomes

of interest will be the proportion of patients with an LDL-C <70 mg/dL and the proportion with an LDL-C <55 mg/dL. An exploratory endpoint, in an optional extension phase, we will assess the rates of long-term outcomes, specifically the rate of major adverse cardiac events (MACE) defined as hospitalization for myocardial infarction, cerebrovascular accident/transient ischemic attack, or coronary or peripheral arterial revascularization. All outcomes will be abstracted from the patient chart via medical record review.

Additional outcomes will collect provider education and experience metrics. We will assess the percentage of providers who visit the guideline site via the link provided within the alert. Further, all providers will be asked to complete both a pre- and post- study survey that will assess their knowledge of and the level of comfort with the ACC/AHA guidelines for hyperlipidemia. The post survey will also include questions that will allow us to assess provider approval and overall acceptance of the alert, assessing their opinions on user friendliness, usefulness versus disruptiveness, and overall user experience. Analysis of responses will allow us to assess which aspects of the alert were most helpful and which could be improved in possible future iterations of this alert and others.

Alerts will no longer be seen by providers and removed from Epic once enrollment is complete but may be reinstated should our data and further study prove that such alerts are useful and beneficial to the patient population.

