Objectives and Endpoints: The objective of this study is to evaluate the efficacy of targeted electronic alerts to improve rates of best practices in the treatment of patients with hyperlipidemia who are seen by outpatient cardiology and internal medicine physicians. The primary outcome will be the proportion of patients who have intensification of their lipid lowering therapy (increase in statin dose or addition of ezetimibe or addition of a PCSK9 inhibitor) at 90-days. The secondary outcomes will be achieved LDL-C (fasting or non-fasting) at 6-months and rates of hospitalization for myocardial infarction, stroke, unstable angina, coronary or peripheral artery revascularization.

Consent and Survey distribution: Provider consent will be collected in one of several ways, and we are requesting a waiver of documentation of consent for providers in this study, as the study poses minimal risk. The first method for provider outreach and consent will be done through university email in which a link to the consent and provider survey will be provided. In this method, the consent and survey will be administered electronically via REDCap (Research Electronic Data Capture) and an electronic signature will be captured. This link to the consent form will be sent to all eligible providers that will direct them to our online consent form in REDCap for review and signature. If the provider consents, we will follow up and send a survey link that will direct them to the survey form in REDCap.

Should provider outreach via email prove difficult, we will use other means to contact eligible providers. The first will be via an Epic inbasket message, where the informed consent will be copied directly into the body of an Epic message that is then sent to the eligible provider. The provider can then read through the consent and reply back to the inbasket message with "Yes I do consent" or "No I do not consent", without requiring a signature on the consent document. This response will be document, and consented providers will then be sent further instructions and a link for the REDCap survey.

We will also contact providers via telephone, where study personnel will describe the study via phone, answer questions, and receive and document provider verbal consent. Consented providers will then be sent further instruction and a link for the REDCap survey.

If/when feasible, study coordinators will also conduct in-person recruitment to obtained signed consent.

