Other aggregate analyses (any report containing Safety data generated during the course of the study)	At the time of Sponsor submission to any body governing research conduct (eg. RA, IRB etc.)	NASCR Manager
 Final (End of Study Report, including): Unblinding data for blinded studies Reports of unauthorized use of a marketed product 	At the time of Sponsor submission to any body governing research conduct (eg. RA, IRB etc.) but no later than 1 calendar year of study completion	NASCR Manager

9. Statistical Considerations:

Initial review of retrospective data for calendar year 2017 revealed 35,472 unique individuals who underwent LDL testing at a Yale-affiliated practice. Of those, 4,451 had ASCVD (one ICD-10 code) and LDL-C > 70mg/dL. The following graphic displays the cumulative number of unique eligible patients attained (y-axis) by interfacing with a given number of providers (x-axis), starting with the provider who sees the most patients meeting inclusion criteria.

As displayed above, clusterrandomization of the top 100 providers (in terms of number of patients with high-LDL seen; at least 10 per week) would include approximately 3700 unique patients and we are proposing to enroll 2500 patients over 9 months. Randomizing 100 providers (50 in the alert group and 50 in the control group with an equal number of cardiology and internal medicine providers in each arm - 25 patients per provider) would give 80% power to detect a difference in intensification of lipid lowering therapy from 5% (current ezetimibe rate) to 9.3% and 90% power to detect a difference from 5% to 10.7%, assuming

a conservative intra-class correlation coefficient of 0.05. Similarly, we would have 80% power to detect an increase in PCSK9 inhibitor use from <0.2% to 1.9% and 90% power to detect an increase from <0.2% to 2.4%. The primary analysis will be conducted using logistic regression where the independent variable (primary endpoint) is the proportion of the patients who have intensification of their lipid lowering therapy and the primary dependent variable is randomization status. The regression will be clustered at the provider level.

SECTION II: RESEARCH INVOLVING DRUGS, BIOLOGICS, RADIOTRACERS, PLACEBOS AND DEVICES

If this section (or one of its parts, A or B) is not applicable, check off N/A and delete the rest of the section.

A. RADIOTRACERS MN/A

B. DRUGS/BIOLOGICS MN/A

B. DEVICES **N/A**

SECTION III: RECRUITMENT/CONSENT AND ASSENT PROCEDURES

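### The primary logistic model names no covariates, although specialty and each provider's pre-randomisation prescribing will be known

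*Combined protocol and SAP*

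**What the plan says.** The primary model is set out in two sentences of Section I, 9. Statistical Considerations. It is a logistic regression "where the independent variable (primary endpoint) is the proportion of the patients who have intensification of their lipid lowering therapy", and the text continues: "the primary dependent variable is randomization status. The regression will be clustered at the provider level". The word primary attached to arm may hint at further terms, but none is named there or elsewhere, so the model as written is unadjusted.

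Elsewhere intensification is plainly the outcome. The Research Plan has "Our primary outcome will be proportion of patients with intensification of lipid lowering therapy" and Objectives and Endpoints has "The primary outcome will be the proportion of patients who have intensification of their lipid lowering therapy", both at 90 days.

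Two provider characteristics will be known before any patient is enrolled:

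- **Specialty.** The sample-size text in Section I, 9 describes randomising 50 providers per arm "with an equal number of cardiology and internal medicine providers in each arm".
- **Baseline prescribing.** The Research Plan says: "Once consented, we will determine baseline prescribing patterns for lipid lowering therapy". This covers three months and precedes randomisation. It records the share of very-high-risk patients on high-intensity statin, ezetimibe or a PCSK9 inhibitor, and the LDL-C distribution. Its only stated analytic use is that pre/post "analyses in the control group, leveraging the three-month baseline period, can assess the level of contamination" and secular trend.

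**The concern.** With 100 randomised units and an ICC of 0.05, differences between providers make up much of the variance of the treatment comparison. Anything known before randomisation that predicts a provider's tendency to intensify can remove part of that variance. Specialty and prior prescribing are natural candidates. The plan treats the first as something to balance and collects the second, yet the primary model uses neither. What is at stake is precision, together with having the covariate set fixed before results by arm are seen.

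The swapped labels belong to the same point, because they cease to be harmless once covariates enter the model. The term used for clustering also needs one clarifying phrase.

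**Working it through.** **1. Inputs.** From Section I, 9: 50 providers per arm, 25 patients each (1,250 per arm), ICC 0.05, 5% against 9.3%, stated power 80%. Assumed, because the documents do not state it: two-sided 5% level. Also assumed: R², the share of between-provider variance that the covariates explain.

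**2. The plan's own figure.** The design effect is 1 + (25 − 1) × 0.05 = 2.2, so the effective size per arm is n = 1250/2.2 = 568.2. With mean proportion p̄ = (0.05 + 0.093)/2 = 0.0715,

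power = Φ{[(p2 − p1) − 1.96·√(2p̄(1 − p̄)/n)] / √([p1(1 − p1) + p2(1 − p2)]/n)}

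= Φ{(0.043 − 0.02996)/0.01523} = Φ(0.856) = 80.4%. The stated 80% reproduces.

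**3. With covariates.** Adjustment shrinks only the between-provider part of the variance, so the factor 2.2 becomes 25 × [0.05(1 − R²) + 0.95/25]. The same power formula is applied to 1250/factor:

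| R² (assumed) | factor | effective n per arm | power |
|---|---|---|---|
| 0 | 2.2 | 568.2 | 80.4% |
| 0.02 | 2.175 | 574.7 | 80.8% |
| 0.05 | 2.1375 | 584.8 | 81.5% |
| 0.10 | 2.075 | 602.4 | 82.6% |
| 0.25 | 1.8875 | 662.3 | 86.0% |

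Simulation (5,000 trials per setting, exchangeable working correlation, assumed coefficient of variation of provider size 0.6) shows the same pattern. Adjusted against unadjusted power is 78.2% against 77.7%, 78.7% against 77.1%, and 82.1% against 78.5% at R² 0.05, 0.10 and 0.25.

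**4. Cost if the covariates explain nothing.** At R² = 0, simulated power is 79.6% adjusted against 80.3% unadjusted with equal provider sizes (4,000 trials), and 77.1% against 78.0% at a coefficient of variation of 0.6 (5,000 trials). The loss is 0.7 and 0.9 points.

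**5. The swapped labels.** An odds ratio from a 2×2 table is the same whichever variable is called the outcome. In simulation, an unadjusted logistic model with provider-robust standard errors gave the same log odds ratio in both directions (largest gap under 1e-13) and the same mean standard error. With covariates added, the two directions differed by a mean log odds ratio of 0.005 to 0.013 and disagreed on significance in 0.5% to 0.9% of trials (1,500 trials at each of R² 0.05, 0.10 and 0.25). The labels should therefore be corrected when covariates are added.

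**6. The clustering term.** A pooled logistic model with provider-robust standard errors and an exchangeable GEE coincide when all providers contribute equally, as the 25-per-provider assumption implies. The plan also ranks providers by volume, "starting with the provider who sees the most patients meeting inclusion criteria", and states no cap, so sizes may differ. At assumed coefficients of variation of 0.3, 0.6 and 0.9, simulated power is 79.4%, 75.2% and 68.5% for the first model and 80.2%, 78.0% and 72.7% for the second. They disagree on significance in 4.1%, 8.0% and 11.9% of trials.

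**The case against.** An unadjusted analysis of a randomised comparison is valid, so adjustment can be called a preference. The gain may also be slight. At R² = 0.05 the simulated rise from 77.7% to 78.2% is within Monte Carlo error of about 0.6 points per estimate. The 86.0% figure needs a 25% share that nothing in the documents supports, and the baseline measures how many patients are already on therapy, not how often therapy is stepped up. All of this stands, and it limits the size of the claim. It does not remove the case for adjusting: the data are already planned, no bias is introduced, and the worst case costs less than one point of power.

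A reader might infer three stronger things that the documents do not support.

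- **That the reversed labels invalidate the primary analysis.** The model sentence itself tags intensification as the primary endpoint, and every other section treats it as the outcome. It is a wording slip that changes no result under the natural reading. A reversed exchangeable GEE does break down (odds ratio 1.00002), but only because arm is constant within provider, and nothing suggests that anyone intends that model.
- **That the open estimator puts type I error at risk.** Running both models and reporting whichever is significant gave up to 8.8%, against 6.5% for the exchangeable model alone, at an assumed coefficient of variation of 0.9. Nothing in the plan proposes that practice. The volume graphic in Section I, 9 is not visible in the text available here, so the spread of provider sizes is an assumption. The formula gap at 0.9 (64.4% against 73.0%) is also wider than the simulated one (68.5% against 72.7%).
- **That an exchangeable GEE is required.** The plan defines the outcome as a proportion of patients. Exchangeable weighting gives high-volume providers less weight than a patient average does, so choosing it is a trade-off.

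**Conclusion.** The point holds as a matter of precision. The primary model leaves out two provider-level variables that the plan already balances on or measures. Including them would move power from 80.4% to somewhere between 80.8% and 86.0% if they explain 2% to 25% of between-provider variance, and would cost under one point if they explain nothing. These figures rest on the plan's sample-size values, an assumed two-sided 5% level and assumed shares. The lower end may be the more realistic, since the baseline is prevalence of therapy. Leaving the variables out does not bias the comparison. The label swap is an editorial correction, and the clustering estimator is a clarification; neither shows that the planned analysis is wrong.

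**What to change.** Reword the primary-analysis paragraph in Section I, 9 before unblinding:

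- Keep the logistic regression clustered at the provider level. Make intensification at 90 days (yes/no for each patient) the dependent variable and the provider's randomised arm the independent variable.
- Adjust for specialty and for the provider's baseline proportion of very-high-risk patients on high-intensity statin, ezetimibe or a PCSK9 inhibitor. Report the unadjusted model as a sensitivity analysis.
- As a clarification, name the single estimator meant by clustering, for example provider-robust standard errors with a stated small-sample correction. An exchangeable GEE is optional, because it changes how providers are weighted.
- Also as a clarification, say whether the permuted blocks are stratified by specialty. The Research Plan names no strata. If they are stratified, having specialty in the model also avoids a conservative test.

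The cost is one paragraph, with no extra patients, visits or data. The downsides are the possible loss of under one point of power and an odds ratio that becomes conditional on the covariates (in simulation about 1.97 unadjusted against 1.99 adjusted at a 25% share).
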